4.19. Handling of tabulations for articles

Regarding "Depression, suicidal ideation, suicide attempt", the analysis plan to collect additional CRFs and perform an exploratory analysis of risk factors is attached in Appendix 6 for patients other than patients whose CRFs were collected (Registered patients whose CRFs were collected and patients eligible for CRF collection were identified (administration of this drug started by October 31, 2018)) who developed these events.

In this analysis plan, the specifications for tabulation for literature are also described in common with the stability report, etc., but the details of the analysis plan for the additional analysis based on the collection of additional CRFs will be followed. If the specifications of the stability report and output form are different, the description in the English version of the mock prepared for the paper shall take priority.

Analysis sets:

Since "Supplemental Form (CRFs whose collection started in October 2023 or later: However, patients subject to continuous collection are not considered as additions.)" are collected only from patients with events related to "Depression, suicidal ideation, suicide attempt," they cannot be combined with existing survey data (survey data based on survey form data collected before September 2023) to determine the incidence, etc. and will be used for risk factor analysis. Therefore, it is specified as "excluded from safety analysis (others [safety])" in the periodic safety update report and reexamination application documents submitted to PMDA after June 2024.

Adverse events in the tabulation for literature in the final report: Adverse events excluding those from the follow-up site survey will be tabulated according to 4.15: Adverse events observed by Week 52 of the observation period.

5. STATISTICAL CONSIDERATIONS

5.1. Summary statistics

Refers to sample size, mean, standard deviation, minimum, 25% point, median, 75% point, and maximum.

5.2. Change, percent change, percentage

The change, percent change, and percent change from baseline will be calculated using the following formula. Baseline for average daily steroid dose includes the start date of treatment.

[figure not shown]
- ✧ Change = measured value at each observation time point - measured value at baseline
- ✧ Percent change (%) = (Change/measured value at baseline) x 100
- ✧ Percentage (%) = (Number of patients/Number of patients analyzed) × 100

5.3. Display of Results

The tabulation results shall be presented as follows.

Classification	Display digit
Percent change, percentage	Round off to 1 decimal place.
Number of subjects	Display as whole number.
Mean, standard deviation, 25% point, median, 75% point, confidence interval	Round off the second digit below the number of digits to be displayed and display to the first digit below the number of digits to be displayed.
Min, Max	Round off to the same number of digits to be displayed.
Odds ratio, confidence interval for odds ratio, correlation coefficient	Round off to three decimal places.

5.4. Exploratory analysis of influencing factors

PPD

PPD

5.5. Incidence rate based on person-year method

- ✧ Incidence rate per X patient-years = number of events \times X/patient-years of observation.

Unless otherwise specified, X=100.

- ✧ Person-years of observation (Total Patient-Years) is defined as the sum of duration of treatment with this drug calculated for each analysis population (duration of treatment with this drug = date of completion of treatment with this drug - date of initial treatment with this drug + 1).

6. Primary analysis items

6.1. Patient composition

6.1.1. Patient composition (Figure 1.01)

Analyzed:	-
Analysis details:	
The following numbers of patients, numbers of patients excluded, and reasons for exclusion will be shown using a flow chart.
 
If there are multiple reasons for exclusion in the same patient, they will be summarized in the item of higher priority.
 
The number of study sites will be tabulated for each study site, regardless of clinical department.
 
< All subjects >
 
• Registered sites• Enrolled patients• CRF uncollected• CRF collection facility• Patients whose CRFs were collected• CRF unfixed patients• CRF locked facility• Patients with locked CRF• Patients excluded from safety analysis• Number of sites• Safety analysis population• Patients excluded from efficacy analysis• Efficacy analysis population 
For patients whose CRFs were collected, patients whose CRFs were locked, and patients in the safety analysis set, the number of patients will also be calculated for each CRF volume.

6.1.2. Patient composition (Figure 1.012)

Analyzed:	-
Analysis details:	
The following numbers of patients, numbers of patients excluded, and reasons for exclusion will be shown using a flow chart.
 
If there are multiple reasons for exclusion in the same patient, they will be summarized in the item of higher priority.
 
The number of study sites will be tabulated for each study site, regardless of clinical department. [Analysis for lifting of approval conditions]
 
< All subjects >

- Registered sites
- Enrolled patients
- Institutions where survey forms are collected
- CRF collection target patients
- CRF uncollected
- CRF collection facility
- Patients whose CRFs were collected
- CRF unfixed patients
- CRF locked facility
- Patients with locked CRF
- Patients excluded from safety analysis
- Number of sites
- Safety analysis population
- Patients excluded from efficacy analysis
- Efficacy analysis population

For patients whose CRFs were collected, patients whose CRFs were locked, and patients in the safety analysis set, the number of patients will also be calculated for each CRF volume.

6.2. Patient demographics and baseline characteristics

6.2.1. Composition ratio of patients and summary statistics (Table 1.02x, 1.021x, 1.022x, 1.024x, 1.026x)

Analyzed:	Safety analysis set, efficacy analysis set
Analysis details:	
The number of patients and composition ratio (%) and/or summary statistics will be calculated for each analysis set by patient background factor.
 
Unless otherwise specified, the denominator for the composition ratio (%) will be the total of each analysis set.
 
For patient demographics, baseline values (summary statistics), and laboratory test values (summary statistics), the same analyses will be performed for each initial route of administration (IV, SC) (safety analysis set).

Patient characteristics	
< Category >
 
 • Gender (Male, Female) • Age 1 [years] (<15, 15 ≤ to <65, 65 ≤, unknown) • Age 2 [years] (<45, 45 ≤ to <65, 65 ≤ to <75, 75 ≤, unknown) • Reason for use of this drug 1(Treatment of patients with systemic lupus erythematosus (SLE) who have inadequately responded to conventional treatments and other) 
If there are SLE and other reasons for use, SLE will be tabulated with priority.
 
SLE cases (Severe lupus nephritis, severe central nervous system lupus)

If multiple symptoms are selected, they will be counted multiple times.

- Reason for use of this drug 2(Treatment of patients with systemic lupus erythematosus (SLE) who have inadequately responded to conventional treatments and other)

If multiple symptoms are selected, they will be counted multiple times.

- Autoantibodies associated with SLE (Antinuclear antibody, anti-dsDNA antibody, anti-Sm antibody, lupus anticoagulant, anti-cardiolipin antibody, and other autoantibodies related to SLE)

antinuclear antibody (Positive, Negative), anti-dsDNA antibody (Positive, Negative), anti-Sm antibody (Positive, Negative), lupus anticoagulant (Positive, Negative), anti-cardiolipin antibody (Positive, Negative), and other autoantibodies related to SLE (Positive, Negative)

- Duration of SLE (<5, 5 ≤ to <10, 10 ≤ to <15, 15 ≤ to <20, 20 ≤, unknown)
- Weight [kg] (<30, 30 ≤ to <40, 40 ≤ to <50, 50 ≤ to <60, 60 ≤, unknown)
- Status of vaccination (24 weeks before the start of administration of this drug) (absent, present, unknown)

Breakdown of vaccination (Use of pneumococcal vaccine, influenza vaccine, HPV vaccine, hepatitis A vaccine, hepatitis B vaccine, varicella zoster vaccine, or other vaccines)

- Past history (Tuberculosis, hepatitis B)

If multiple symptoms are selected, they will be counted multiple times.

- Mean daily dose of steroid at the start of treatment [mg/day] (0, 0< to ≤ 7.5, 7.5<, unknown)
- Mean daily dose of steroid at the start of treatment 2 [mg/day] (0, 0< to ≤ 5, 5< to ≤ 10, 10<, unknown)

- Pregnancy (No, Yes)
- Prior treatment for SLE (Steroids, immunosuppressants, antimalarials, NSAIDs, other biologics, cyclophosphamide intravenous injection) (No, Yes)
- Prior medications for SLE (Steroids, immunosuppressants, antimalarials, NSAIDs, other biologics, cyclophosphamide intravenous injection)
- Presence or absence of concomitant medication (No, Yes)
- Concomitant medication for SLE (Steroids, immunosuppressants, antimalarials, NSAIDs, other biologics, cyclophosphamide intravenous injection) (No, Yes)
- Details of concomitant medications for SLE (Steroids, immunosuppressants, antimalarials, NSAIDs, other biologics, cyclophosphamide intravenous injection)
- Presence or absence of concomitant therapy (No, Yes)
- Complications (No, Yes)
- Presence or absence of complication (renal impairment) (No, Yes)
- Presence or absence of complication (hepatic impairment) (No, Yes)
- Complication (allergy) (No, Yes)
- Status of administration of this drug at the end of the observation period (Continuation of administration, discontinuation/completion of administration)

< Summary statistics >

	
 • Age [years] • Age [years] (children: < 15 years) • Age [years] (elderly: ≥ 65 years) • Mean daily dose of steroid at the start of treatment [mg/day] • Duration of SLE [year] • Weight [kg]
Baseline	
< Category >
 
 • SELENA SLEDAI score (≤ 9, $10 \leq$, unknown) • Each item of SELENA SLEDAI • PGA score ($0 \leq$ to ≤ 1, $1 <$ to ≤ 2.5, $2.5 <$ to ≤ 3, unknown)
	
< Summary statistics >
 
 • SELENA SLEDAI score • PGA score • Lupus Impact Tracker
Laboratory	< Category >
Evaluations	
 • Anti-dsDNA antibody [IU/mL] (Negative, Positive (≥ 30 IU/mL), Unknown) • Complement Levels: 
 Low C3 and/or Low C4 Other than the above Unknown • C3 (baseline) [mg/dL] (<90, $90 \leq$, unknown) • C4 (baseline) [mg/dL] (<10, $10 \leq$, unknown)
	
< Summary statistics >
 
 • Anti-dsDNA [IU/mL] • C3[mg/dL] • C4[mg/dL] • CH50[U/mL] • Protein-creatinine ratio [g/g • Cr]
Screening test	
< Category >
 
 • Tuberculosis Screening Prior to Initiation of this drug 
 Presence or absence of chest imaging, tuberculin test, and interferon-γ release assay (No, Yes) Chest imaging/presence or absence of tuberculosis (If absent or present, by active tuberculosis or old tuberculosis), including findings of old tuberculosis PPD skin test/positive status (Negative, Positive) Interferon-gamma release assay/positive status (Negative, Positive) • Hepatitis B screening prior to initiating this drug 
 Presence or absence of HBs antigen, HBs antibody, HBc antibody, and HBV-DNA quantification (No, Yes)

		HBs antigen/positive status (Negative, Positive)
		HBs Ab/positive status (Negative, Positive)
		HBc Ab/positive status (Negative, Positive)
		• Patients with special surveillance item (reactivation of hepatitis B virus)
		HBs antigen, HBs antibody, HBc antibody, and HBV-DNA assay in patients with priority investigation item (reactivation of hepatitis B virus) (Yes)
		< Summary statistics >
		• HBV-DNA, quantitative [Log IU/mL]
Proper status	use	< Category >
		• Prior medications for SLE (Steroids, immunosuppressants, antimalarials, NSAIDs, other biologics, cyclophosphamide intravenous injection)
		Prior treatment for SLE (No, Yes)
		SELENA SLEDAI score by presence/absence of prior treatment for SLE ($0 \leq$ to <4 , $4 \leq$ to <10 , $10 \leq$ to <12 , $12 \leq$, not judged)
		Prior medications for SLE (Steroids, immunosuppressants, antimalarials, NSAIDs, other biologics, cyclophosphamide intravenous injection)
		• Autoantibodies associated with SLE
		Antinuclear antibody or anti-dsDNA antibody (Positive (antinuclear antibody [positive] and/or anti-dsDNA [positive]), negative, or not done)
		SLE-related autoantibodies (antinuclear or anti-dsDNA [negative or not performed]): other autoantibodies (positive) (overlapping) (Anti-Smith, lupus anticoagulant, anticardiolipin, and other autoantibodies associated with SLE), negative for all or not performed

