The study will include all patients to whom Benlysta is administered (except patients aged <15 years who start Benlysta administration since approval for paediatric dosage*). In addition, among patients who start the administration after launch, those to whom Benlysta has already administered before the conclusion of the contract and those who has already started administration at diagnosis, because of hospital transfer, etc. will be included as well.

* : Because the study for paediatric patients is separately conducted following approval for paediatric dosage

The [INDICATIONS] of PRECAUTIONS CONCERNING INDICATIONS of Benlysta are as follows (For details, see the latest Package Insert).

< Revised: October 2019 (Version 4), excerpts from the Package Insert >

【INDICATIONS】

Patients with systemic lupus erythematosus (SLE) who inadequately respond to existing treatments

PRECAUTIONS CONCERNING INDICATIONS

1. Administer Benlysta to patients additionally if they have disease activity even if they are treated for SLE appropriately with steroids and immunosuppressants etc. in the past.
2. Use Benlysta in SLE patients who are confirmed positive for autoantibodies, such as anti-nuclear antibody and anti-double stranded DNA (anti-dsDNA) antibody.

3. In clinical studies, the effectiveness and safety of Benlysta have not been investigated in SLE patients with severe lupus nephritis or severe central nervous system (CNS) lupus (See "CLINICAL STUDIES" section).
4. In clinical studies, the effectiveness and safety of Benlysta have not been investigated in combination with other biologics or intravenous cyclophosphamide (See "CLINICAL STUDIES" section).
5. Be well informed about the contents of "CLINICAL STUDIES" section and have good understanding of the effectiveness and safety of Benlysta and select appropriate patients (See "CLINICAL STUDIES" section).

4. Target Sample Size and Rationale

- 1) Target number of patients : 600 (as a safety analysis set)
- 2) Rationale : Benlysta may increase sensitivity to infections due to the mechanism of action. In clinical studies, there were some reports of patients who had a fatal course. Focusing on serious infections, the incidence rates of the serious adverse event (AE) "Infections and Infestations" (SOC) were 5.3% (25/470 patients) and 4.1% (23/556 patients) in the phase III international joint studies [Study BEL113750 (intravenous administration) and Study BEL112341 (subcutaneous administration)], respectively.

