Under the assumption that the incidence rate of the serious infections is 5.3% as a threshold on the basis of the results of the phase III international joint studies, 553 patients are required to monitor the incidence rate in the post-marketing surveillance with estimation accuracy that enables a power for the 5.3% threshold to be $\geq 80\%$ in case where the real risk exists 1.5 times or more of the threshold. It is considered possible to evaluate occurrence of the serious infections in the special DUI (SDUI) having 600 patients as a target sample size.

The incidence rate of ADRs occurring in one patient was 0.2% in the phase III international joint studies. The power to detect an ADR whose incidence rate of 0.2% is 69.9% in at least one patient out of 600 patients.

5. Planned Number of Medical Institutions by Department

All medical institutions where Benlysta is prescribed (except medical institutions that prescribe Benlysta only for patients aged <15 years since approval for paediatric dosage)

6. Study Period

1. Study conduct

Study period : launch date of Benlysta to three months after termination of the observation period in patients eligible for case report form (CRF) collection (period of the follow-up investigation, if conducted) or lifting date of approval conditions, whichever comes later

Observation period :

The observation period per patient will be 52 weeks from the start of Benlysta administration.

For patients who continue administration at the end of the observation period, conduct the two-year follow-up investigation as much as possible, and monitor occurrence of AEs leading to death, serious infections, PML, and MT.

If a patient has withdrawn from /terminated administration of Benlysta, it will be until the withdrawal/termination.

Scheduled enrolment period : launch date of Benlysta to six months after lifting of approval conditions

Patients are eligible for CRF collection when starting Benlysta administration by 31 October, 2018, and CRFs will be collected as required when patients start the administration since 1 November, 2018. Additionally, patients are eligible for enrolment when starting the administration by the acknowledgment of the report at a committee meeting, where the all-case investigation-related conditions for approval are lifted (except patients aged <15 years who start Benlysta administration since approval for paediatric dosage), and enrolment will continue.

2. Study end

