- (3) Confirm the presence or absence of infection tuberculosis by performing interferon-gamma release assays and timely chest computed tomography, etc. in addition to sufficient interviews and chest X-ray tests for tuberculosis prior to administration of Benlysta. Consult with experienced physicians in diagnosing tuberculosis if patients have a history of tuberculosis and suspected infection tuberculosis. For any of the following patients, administer appropriate antituberculosis drugs prior to administration of Benlysta, in principle.

1) Patients with an estimated shadow consistent with old tuberculosis on chest image test

2) Patients with a history of tuberculosis treatment (including extrapulmonary tuberculosis)

3) Patients who are strongly suspected of having been previously infected by tests such as interferon-gamma release assays

4) Patients with a history of close contact with tuberculosis patients

In addition, extra caution should be exercised regarding occurrence of tuberculosis, for example, perform regularly appropriate tests, such as chest X-ray tests during administration of Benlysta, and instruct patients to contact their attending physicians immediately if suspected symptoms of tuberculosis occur (persistent cough, pyrexia, etc.). Do not administer Benlysta if active tuberculosis has been confirmed.

*: Described in “2. IMPORTANT PRECAUTIONS (4)” in the Package Insert for subcutaneous use.

4. Screening test regarding HB before the start of administration

Presence or absence, and results of testing for HBs antigen, HBs antibody, HBc antibody, HBV-DNA quantification

<Related descriptions in the Package Insert (For details, see the latest Package Insert)>

<Revised: October 2019 (Version 4), excerpts from the Package Insert>

2. IMPORTANT PRECAUTIONS (for intravenous use)*

- (6) Confirm the presence or absence of HB virus infection prior to administration of Benlysta as hepatitis associated with reactivation of HB virus may occur in patients who are HB virus carriers or have been previously infected with HB virus (HBs antigen negative, and HBc antibody or HBs antibody positive).

If Benlysta is administered to patients who are HB virus carriers or have been previously infected with HB, caution should be exercised regarding occurrence of signs and symptoms of reactivation of HB virus, for example, monitor hepatic function test values and hepatitis virus markers.

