2) Physician's Global Assessment (PGA)

Record the presence or absence of assessment, assessment date, results of assessment at the start date of administration, Week 24 and 52 after the start of administration, or withdrawal/termination.

The PGA is a 0-10 cm visual analogue scale (VAS). The investigator will assess the patient's global disease activity, and draw a vertical line between 0 CCI and 3 CCI (See Appendix 2).

0 : CCI

1 : CCI

2 : CCI

3 : CCI

3) Assessment of Daily Living by Lupus Impact Tracker

Record the presence or absence of assessment, assessment date, results of assessment at the start date of administration, Week 24 and 52 after the start of administration, or withdrawal/termination.

The investigator will interview patients about their conditions in the previous one month using Lupus Impact Tracker, the impact on daily living will be assessed using a 5-point scale of 0 CCI to 4 CCI

CCI - This section contained Clinical Outcome Assessment data collection questionnaires or indices, which are protected by third party copyright laws and therefore have been excluded.

* 0 : CCI 1 : CCI 2 : CCI
3 : CCI 4 : CCI

12. Laboratory tests

1) Monitoring for TB (if a patient has TB as a past history)

Presence or absence, test date, results of chest image test and interferon-gamma release assay (The chest image test includes the presence or absence of findings of activity.)

2) Monitoring for HB (if a patient is a HB virus carrier or has a past HB infection)

- Presence or absence, test date, results of HBV-DNA quantification test and hepatic function test (aspartate aminotransferase (AST), alanine aminotransferase (ALT))
- 3) The information about the following items will be collected.
- Presence or absence of assessment, assessment date, results of assessment at the start date of administration*, Week 24 and 52 after the start of administration, or withdrawal/termination
- * : If no information is available about the results of assessment at the start date of administration, record the information closest to the start date in the results of SLE diagnosis to the start date.
- i) Immunological test
Anti-double-stranded DNA (anti-dsDNA) antibody, C3, C4, CH50
 - ii) Renal function test
Protein/creatinine ratio
13. Continuation status of Benlysta administration at the end of the observation period

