6.3.8. Incidence of adverse drug reactions/adverse events (Table 2.09xx, 2.11)

Analyzed:	Safety analysis population
Analysis details:	
For adverse drug reactions/adverse events by seriousness (serious/all), the incidence of PT based on the person-year method and the proportion of PT by number of patients will be tabulated. As for the order of output, data should be output in the descending order of the number of PTs in the overall column of adverse events and in the order of PT codes (if the number of PTs is the same).
 
Safety specifications will be prepared in the same manner.
 
The person-year method shall be prepared in accordance with the "5.5. Incidence rate calculated using person-year method."

Safety Specification:	"Safety Specification "

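### Hepatitis B reactivation is reported only over the whole safety set; the visible SAP has no at-risk denominator and no summary of on-treatment HBV-DNA, AST and ALT

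*SAP*

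**What the plan says.** Protocol section 2 names HB reactivation as a safety concern and priority study matter. Section 8, item 4, collects screening for HBs antigen, HBs antibody, HBc antibody and HBV-DNA. Its package-insert excerpt names two groups in whom reactivation may occur: carriers, and previously infected patients ("HBs antigen negative, and HBc antibody or HBs antibody positive"). For those two groups, item 12 collects during treatment "Presence or absence, test date, results of HBV-DNA quantification test and hepatic function test", the latter being AST and ALT. The planned size in section 4 is "Target number of patients : 600 (as a safety analysis set".

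On the analysis side:

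- SAP 5.2 divides every percentage by the number of patients analysed. SAP 6.3.3, 6.3.6 and 6.3.8 work in the safety analysis population, and 6.3.8 adds "Safety specifications will be prepared in the same manner". The person-year rate in 5.5 uses the summed treatment time of the analysis population.
- The specific-background breakdowns in 6.3.3 and 6.3.6 are age, pregnancy, renal impairment and hepatic impairment. HB status is not among them.
- SAP 6.2.1 tabulates each HB marker singly at screening, then "HBs antigen, HBs antibody, HBc antibody, and HBV-DNA assay in patients with priority investigation item (reactivation of hepatitis B virus) (Yes".
- The laboratory outputs over time (6.4.7, 6.4.15) cover anti-dsDNA, C3, C4, CH50 and protein/creatinine ratio.

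**The concern.** By the protocol's own account, reactivation concerns carriers and previously infected patients. A proportion over the whole safety set mixes them with patients outside that group. If few or no cases occur, the whole-set figure shows little about the patients who carry the risk. Protocol section 13 makes the proportion of occurrence and the risk factors inputs to a possible Package Insert revision, so the denominator has consequences.

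The laboratory data that could show how closely at-risk patients were watched, and what was found, are collected but reach no visible output. SAP 4.15 defines adverse events as those entered in the safety database. A rise recorded only in the laboratory fields of the CRF would therefore not be counted.

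The SAP restricts denominators where it sees a need. Steroid-reduction outputs take only patients above 7.5 mg/day at baseline, and organ-system improvement needs a baseline score above 0. The proper-use part of 6.2.1 even builds a composite marker group (antinuclear and/or anti-dsDNA positive). HB status gets no such treatment.

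**Working it through.** **1. The plan's own figure.** Protocol section 4 states: "The power to detect an ADR whose incidence rate of 0.2% is 69.9% in at least one patient out of 600 patients". The check is 1 − (1 − 0.002)^600 = 0.699, so the figure reproduces. It applies to an event that can occur in any of the 600.

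**2. Input the documents do not give.** The share of patients who are HB carriers or previously infected appears nowhere. I assume 5% to 30%, that is 600 × 0.05 = 30 to 600 × 0.30 = 180 patients.

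**3. What zero cases would exclude.** The exact one-sided 95% upper bound for zero events in n patients is 1 − 0.05^(1/n). The last column is the chance of at least one case at a 0.2% risk, 1 − 0.998^n.

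| Denominator | n | Upper bound, zero cases | Ratio to whole set | Chance of at least one case at 0.2% |
|---|---|---|---|---|
| Whole safety set | 600 | 0.50% | 1 | 69.9% |
| At risk, 30% (assumed) | 180 | 1.7% | 3.3 | 30.3% |
| At risk, 20% (assumed) | 120 | 2.5% | 5.0 | 21.4% |
| At risk, 10% (assumed) | 60 | 4.9% | 9.8 | 11.3% |
| At risk, 5% (assumed) | 30 | 9.5% | 19 | 5.8% |

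A single case would be 1/600 = 0.17% of the whole set, against 1/180 = 0.56% to 1/30 = 3.3% of at-risk patients.

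**4. Effect of incomplete monitoring.** If only half of the at-risk patients had an on-treatment HBV-DNA result (a further assumption), the zero-case bound among those tested is 3.3% (n = 90) to 18.1% (n = 15). No visible output gives the number tested.

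**5. What can be recovered from the visible tables.** If a, b and c are the counts positive for HBs antigen, HBs antibody and HBc antibody, the number positive for at least one lies between max(a, b, c) and a + b + c. The upper end can be up to three times the lower, so the bracket can be wide. SAP Table 1.031 (HB as a complication) and Table 2.01 (past history of HB) give adverse reactions of any kind by HB status, not reactivation.

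**The case against.** The strongest reply is that little is lost. Protocol section 8, item 16, requires all adverse events whatever their cause, counts abnormal laboratory values among them, and adds a detailed investigation for priority matters. Reactivations reported that way will be tabulated by safety specification and listed (SAP 6.5). Single-marker counts bracket the at-risk number, and Listing 22 shows who was not screened. With zero cases the estimate is 0% under either denominator, and the visible safety sections specify no confidence limit, so the 0.50% is not a figure the SAP would print. The fold-difference follows directly from an assumed share.

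All of that stands, and it limits the point. It does not supply the union of markers under the protocol's definition, the number monitored, or a count of rises not reported as events. The bounds in the working measure what zero cases could exclude; they do not predict the report.

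Three stronger readings are tempting, and the documents do not support them.

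- *The on-treatment HB results are never analysed.* SAP 5.4 and 6.6 are blacked out, which is no fault of the plan, and protocol section 9 mentions each laboratory test item, though under effectiveness. Only the absence from visible text can be stated.
- *The study cannot answer its question on HB.* The screening and on-treatment data are collected, so the gap lies in the analysis and can be closed.
- *TB recording contradicts the protocol's own at-risk list.* The item 12 trigger is "Monitoring for TB (if a patient has TB as a past history", and the excerpt under item 3 also names "Patients who are strongly suspected of having been previously infected by tests such as interferon-gamma release assays". But that list is introduced as grounds for drugs before starting treatment, not as a monitoring rule. Close contact is not among the screening items. New CRF fields would also come too late for the mandatory cohort: those patients started by 31 October 2018, so their 52 weeks ended around late 2019.

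**Conclusion.** The point holds as a gap in the visible analysis of a named safety specification. The SAP reports reactivation over everyone, forms no composite at-risk group, and shows no summary of the on-treatment HBV-DNA, AST and ALT results. Its one HB-specific output is conditioned on the event.

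The direction is firm, because a whole-set denominator can only make the risk among susceptible patients look smaller. The size is not: a factor of 3.3 to 19 in the zero-case bound rests wholly on an assumed at-risk share of 5% to 30%. Nothing here shows that unreported HBV-DNA rises occurred, only that the visible outputs would not reveal them. The change is worth making before the final report, which protocol section 6 schedules for December 2025.

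**What to change.** Add one table to SAP 6.3, restricted to HB carriers and previously infected patients as the protocol's excerpt describes them and derived from the screening markers. State in the SAP which marker result identifies a carrier, since the excerpt spells out only the previously infected group. Show:

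- the number at risk, with the number whose HB status cannot be determined given beside it;
- the number with at least one on-treatment HBV-DNA result;
- the number whose HBV-DNA became detectable or rose from screening;
- the number with a reported reactivation adverse event, with an exact 95% confidence interval.

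Show HBc-antibody-positive patients separately as well. HBs antibody alone may reflect vaccination; hepatitis B vaccination is recorded, but before treatment only for the preceding 24 weeks.

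Report the table beside the whole-set figure and base the HB reactivation conclusion on it. If the final analysis scheduled for July 2025 has already been run, label the table as added afterwards.

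The cost is one more table, from data already collected, and a wider interval than the whole-set figure would give.
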